10.5.4 Adverse Event Reporting

Adverse events may be volunteered spontaneously by the subject, or discovered as a result of general, non-leading questioning. Adverse events occurring from the time of consent up to the final study visit will be recorded. All AEs should be recorded in the eCRF and in the subjects' source notes.

Any SAE occurring from the time the subject signs informed consent until 30 days after the last dose of IMP must be reported immediately (within 24 hours of the investigator becoming aware of it) and recorded on the SAE Form. Detailed instructions for the reporting of SAEs can be found in the Study Manual. All patients with a SAE must be followed up and the outcomes reported. The investigator must supply the Sponsor and the relevant agency/IRB/IEC with any additional requested information (e.g., autopsy reports and terminal medical reports). Any follow-up information on a previously reported SAE will also be reported within 24 hours of awareness.

If the Investigator does not have all information regarding an SAE, he/ she will not wait to receive additional information before reporting the event and completing the appropriate data collection form. The Investigator will always provide a preliminary assessment of causality at the time of the initial report as described in Section 10.5.3.

The primary mechanism for reporting SAEs will be a paper collection form.

Fax transmission or 'scan & email' of the SAE form is the preferred method to transmit this information to the project contact for SAE receipt. In rare circumstances and in the absence of fax equipment, notification by telephone is acceptable, with a copy of the SAE data collection form

sent by overnight mail. Initial notification via the telephone does not replace the need for the Investigator to complete and sign the SAE data collection form within the designated reporting periods.

NeRRe is required to expedite to worldwide regulatory authorities reports of SUSARs in line with the relevant legislation. Fatal or life-threatening SUSARs must be reported within 7 calendar days and other SUSARs within 15 calendar days.

In accordance with the European Commission Directive 2001/20/EC, NeRRe will notify the relevant Ethics Committees in concerned Member states of applicable SUSARs as individual notifications or through a periodic line listing.

NeRRe will submit to the regulatory authorities all safety updates and periodic reports, as required by applicable regulatory requirements.

All investigators will receive a safety letter notifying them of relevant SUSAR reports. Each Investigator must then notify his or her relevant agency/IRB/IEC of the SAE as required by local regulatory authorities and in accordance with IRB/IEC policy. NeRRe will submit to the regulatory authorities all safety updates and periodic reports, as required by applicable regulatory requirements.

11. STATISTICAL CONSIDERATIONS

The primary objective of the study is to evaluate the efficacy of 10 mg, 20 mg, and 30 mg orvepitant versus placebo in reducing awake objective cough frequency. The corresponding primary endpoint is the change in objective awake cough frequency at Week 12 compared to Baseline and will be analyzed after taking logs (to base 10).

The primary objective will be assessed by testing the following hypotheses for each orvepitant group separately:

Null hypothesis (H0): There is no difference in the mean change in log transformed objective awake cough frequency at Week 12 compared to Baseline for the orvepitant treatment group compared to placebo.

$$H0: \mu(\text{active}) = \mu(\text{placebo})$$

Alternative hypothesis (H1): There is a difference in the mean change in log transformed objective awake cough frequency at Week 12 compared to Baseline for the orvepitant treatment group compared to placebo.

$$H1: \mu(\text{active}) \neq \mu(\text{placebo})$$

Each comparison will be carried out at the two-sided 5% level of statistical significance. No adjustment will be made for the multiple orvepitant versus placebo group comparisons in this

phase 2 study (three in total: 10 mg versus placebo, 20 mg versus placebo and 30 mg versus placebo) with the understanding that this increases the overall type I error rate of the study.

11.1 Estimated Sample Size

The initial planned sample size for this study was 55 subjects per treatment group (220 subjects in total). As a result of the planned sample size re-estimation the sample size is increased to 65 subjects per group (260 in total). The sample size calculation is based on pairwise comparisons of the primary endpoint for each active dose versus placebo. Objective cough frequency will be analysed on a log scale. A two-sided type I error of 0.05, not adjusted for multiple comparisons against placebo, will be used for this exploratory study. Assuming a revised standard deviation of change from Baseline (after taking logs) of 0.285 (based on the sample size re-estimate and increased from the original assumption of 0.261) a reduction in the placebo group of 10% and a reduction in the orvepitant group of 35%, 65 subjects per arm will provide a power of 80%. This new standard deviation estimate has been obtained (at the first sample size review) by considering the full analysis set subjects (as revised, See Section 11.2).

After at least 100 subjects have completed the Week 12 ACM assessment (and in addition to the now completed first sample size re-estimate) the cough frequency data will be reviewed to check the estimate of variability assumed for the primary efficacy variable. This interim sample-size re-estimation will be done on a fully blinded basis using an overall pooled estimate of standard deviation and may result in an increase in the sample size (Kieser and Friede, 2000). Only the awake cough frequency data will be reviewed.

Assuming no further changes to the sample size estimate, approximately 292 subjects will be randomized to ensure at least 260 completers (assuming approximately 10% drop out rate). The sample size may be adjusted again after the second re-estimate and provided no more than 320 subjects (approximately 80 per group) are required the precise number will be documented in a non-substantial (administrative) amendment to the protocol. Any possible impact on the type I error due to this blinded sample size re-assessment procedure is believed to be negligible (Kieser and Friede, 2003).

11.2 Analysis Sets

The following data sets will be used for the statistical analysis.

1. **Safety Set:** All subjects who receive at least one dose of double-blind study drug irrespective of treatment received. Subjects will be analyzed according to treatment received
2. **Full Analysis Set (FAS):** All randomized subjects who received at least one dose of double-blind study drug, irrespective of treatment received, satisfy inclusion criterion number 4 (awake cough frequency of ≥ 10 coughs/hour during the Screening period), and have awake cough frequency data from the ACM for at least one post-treatment assessment. Subjects will be analyzed according to randomized treatment. This is the primary efficacy analysis set for the study.

3. **Per Protocol (PP) Set:** All subjects in the FAS excluding those identified as relevant protocol violators.
4. **Exposure-Response (ER) Set:** all subjects who received at least one dose of double-blind study drug and for whom the PK data are considered sufficient.

Analysis Sets will be identified prior to the unblinding of the study data.

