8.2 Secondary efficacy endpoints

The secondary efficacy endpoints include:

Objective awake cough frequency changes:

- Change in awake objective cough frequency at Weeks 2, and 4 compared to Baseline
- Change in 24-hour objective cough frequency at Weeks 2, 4, and 12 compared to Baseline
- Change in night-time (non-waking time) objective cough frequency at Weeks 2, 4 and 12 compared to Baseline

The validated Quality-of-Life assessment tool the LCQ.

- Change in the LCQ score (total and three domain scores) at Weeks 2, 4, 8, and 12 compared to Baseline

The Cough Severity VAS, the Urge-to-Cough VAS and the Global Rating of Change for Cough Frequency and Severity.

- Change in the Cough Severity VAS at Weeks 2, 4, 8, and 12 compared to Baseline
- Change in the Urge-to-Cough VAS at Weeks 2, 4, 8, and 12 compared to Baseline
- Global Rating of Change in Cough Frequency and Severity at Weeks 2, 4, 8, and 12

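### Section 11.2 ties the primary efficacy set to usable post-baseline cough-monitor data, so read as written it drops some subjects with valid questionnaire data from endpoints that do not use the monitor

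*Protocol*

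**What the plan says.** Section 11.2 of the protocol lists four analysis sets.

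- **Safety Set:** all treated subjects, analysed by treatment received.
- **FAS:** randomised and treated subjects who meet inclusion criterion 4 and "have awake cough frequency data from the ACM for at least one post-treatment assessment", analysed as randomised. Its role is stated without restriction to particular endpoints: "This is the primary efficacy analysis set for the study".
- **Per Protocol (PP) Set**, nested in the FAS: "All subjects in the FAS excluding those identified as relevant protocol violators".
- **Exposure-Response (ER) Set**, selected on PK data: "all subjects who received at least one dose of double-blind study drug and for whom the PK data are considered sufficient".

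Section 8.2 includes secondary efficacy endpoints that do not use the ACM. The LCQ is one: "Change in the LCQ score (total and three domain scores) at Weeks 2, 4, 8, and 12 compared to Baseline". Two further scales (a VAS for severity and a VAS for the urge to cough) and the global ratings of frequency and of severity follow the same four-visit schedule.

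Section 11.5.2 gives their methods (MMRM, with Mantel-Haenszel for the Global Rating) and names no analysis set.

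**The concern.** The ACM condition suits the cough-frequency endpoints. A subject with no post-baseline recording adds nothing to the outcome model there, so the condition costs nothing. For the questionnaire endpoints it works differently. It removes randomised, treated subjects whose outcome was observed, because a different instrument gave no data after randomisation.

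This also sits badly with two other parts of the protocol. Section 7.4 asks sites to keep obtaining efficacy assessments after study drug is stopped, for assignment to the randomised arm. Section 11.8 relies on likelihood methods under missing at random, which draw their strength from using every observed value. What is at stake is a little precision on the patient-reported endpoints and, if ACM failure or refusal is related to treatment, some selection.

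**Working it through.** **1. Which set can hold a randomised comparison of a questionnaire endpoint?**

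| Set (Section 11.2) | Needs post-baseline ACM data? | Usable for a randomised efficacy comparison? |
|---|---|---|
| Safety | No | No: analysed by treatment received |
| FAS | Yes | Yes |
| PP | Yes, as a subset of the FAS | Yes |
| ER | No | No: selected on PK data, for exposure-response |

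Every set that supports such a comparison carries the ACM condition.

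**2. Can an affected subject exist?**

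- Questionnaires are completed during the Week 2, 4, 8 and 12 visits. The ACM is fitted at the end of the Week 2, 4 and 12 visits and records for the next 24 hours (Section 8.5.3). Questionnaire data can therefore exist when the recording from the same visit yields nothing.
- A recording without usable data is foreseen, but a repeat is described only for Screening (Section 8.5.1; Table 1, note g).
- A subject who leaves before Week 2 is not affected. The Early Termination visit has no questionnaires (Table 1), so there is nothing to discard.
- A subject with one usable recording out of three is in the FAS.

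The affected subjects are those with at least one post-baseline questionnaire and no usable recording from any attempt.

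**3. How many?** The plan gives no figure for this, so the size has to be illustrated.

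- Base: Section 11.1 randomises about 292. This reproduces: 65 / 0.90 = 72.2, rounded up to 73 per arm, and 4 × 73 = 292.
- Assumption: each recording fails with probability f, independently, with f from 5% to 20%.
- Assumption: a share e of subjects, 0% to 10%, leave after Week 2 with one recording attempted. All others attempt three.

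Share affected = (1 − e) × f³ + e × f

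| f | e | Share | Of 292 |
|---|---|---|---|
| 5% | 0% | 0.05³ = 0.01% | 0.04 |
| 10% | 5% | 0.95 × 0.001 + 0.05 × 0.10 = 0.60% | 1.7 |
| 20% | 0% | 0.20³ = 0.80% | 2.3 |
| 20% | 10% | 0.90 × 0.008 + 0.10 × 0.20 = 2.72% | 7.9 |

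The range is about 0 to 8 subjects. Most of the upper figure comes from early leavers: 0.10 × 0.20 = 2.0 of the 2.72 percentage points.

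**4. What does that cost?** If a share p is lost evenly across arms, standard errors are multiplied by 1/√(1 − p). At p = 2.72% this is 1/√0.9728 = 1.014, a rise of about 1.4%. In power terms, take a questionnaire endpoint with 80% power at 73 per arm (an assumption, since the protocol powers none of them). Losing 1% of subjects gives 79.6%, and losing 3% gives 78.8%.

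**5. Primary analysis.** It is unchanged. Excluded subjects have no post-baseline ACM value to contribute, and the stated 65 per arm for 80% power does not depend on this rule.

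**The case against.** The strongest objection is that the protocol never says in words that the questionnaire endpoints use the FAS. Section 11.5.2 is silent, and Section 11.3 leaves further analysis detail to the SAP, which was not available for this review. Choosing the population for each secondary analysis is ordinary SAP content. This stands in part: use of the FAS here is an inference, and the SAP may already resolve it. But the entry rule and the set's study-wide role are stated in the protocol, and no alternative is offered. The point is therefore about a rule as written, not about missing detail.

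A second objection is that one population anchored on the primary endpoint is simple, and defensible in a study the protocol calls exploratory. That is a fair preference, but it is bought by discarding observed data.

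A third is that requiring a post-baseline value of the endpoint itself is also a post-randomisation condition. True, but such subjects have no outcome to analyse, so no observed value is lost.

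A reader might also infer more than the protocol supports:

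- *That early leavers in general are lost.* They are not. Those who leave before Week 2 have no post-baseline questionnaire.
- *That the Week 8 visit, which has no ACM, creates a large gap.* A subject who reaches Week 8 would normally have had recordings attempted at Weeks 2 and 4.
- *That the randomised comparison is broken.* Tablets are identical, and subjects, investigators and sponsor are blinded (Section 9.3). Recordings are read centrally in all arms (Section 8.5.3), and the sets are fixed before unblinding (Section 11.2). Nothing in the protocol points to loss that differs by arm.

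**Conclusion.** The point holds as a minor one. On its plain reading, Section 11.2 excludes subjects with valid LCQ, VAS or Global Rating data from those analyses when no ACM recording is usable. Under the stated assumptions this is about 0 to 8 of 292 subjects, with standard errors up to about 1.4% larger.

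Two assumptions carry that size. The failure and leaving rates are illustrative, because the protocol gives neither. Failures are also taken as independent. If they cluster within subjects, for example because someone who refuses the device once tends to refuse again, the share among completers would exceed f³, and the protocol offers nothing to gauge by how much. Bias is a conditional risk only: it needs the loss to differ by arm. The primary analysis and the sample size are untouched.

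**What to change.** In Section 11.2, limit the post-baseline ACM data condition to the cough-frequency endpoints (awake, 24-hour and night-time). For the LCQ, Cough Severity VAS, Urge-to-Cough VAS and Global Rating, define the set as all randomised, treated subjects who meet inclusion criterion 4 and have at least one post-baseline value of that endpoint, analysed as randomised. If the SAP already does this, align the protocol wording with it.

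This takes one sentence, needs no new data, and should be settled before unblinding, when the protocol says the sets are identified. The cost is that N will differ slightly between endpoints and must be shown in each table.

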11.3 Data Analysis

More details of the proposed statistical analysis will be documented in the statistical analysis plan (SAP), which will be written following finalization of the protocol and finalized prior to the breaking of the blind.

For continuous data and for ordered categorical data, if appropriate, the number of non-missing observations, mean, standard deviation, median, first and third quartiles, minimum and maximum will be calculated. For ordered categorical data and nominal data, absolute counts and relative frequencies (in %) will be calculated.

All statistical hypothesis tests and confidence intervals will be two sided, using a type I error rate of 0.05. No adjustment for multiple comparisons will be used for this study.

Raw data will be listed.

11.4 Demographics and Baseline Characteristics

Relevant Screening and Baseline data (i.e. data collected prior to the treatment administration) and demographic characteristics will be summarized descriptively for each treatment group. There will be no formal comparison of Baseline data, that is, no statistical hypothesis testing.

11.5 Statistical Methods for Efficacy Parameters

11.5.1 Primary Efficacy Analysis

Awake objective cough frequency at Baseline and Weeks 2, 4 and 12, along with change from Baseline, will be summarized for each treatment group and for each time point on the original scale (including percent change from Baseline) and after log (base 10) transformation. NB: The Baseline for objective cough frequency outcomes is the measurement obtained during the Screening period.

The primary analysis of log transformed awake objective cough frequency will be conducted via a mixed model for repeated measures (MMRM) with the model including terms for region, baseline log-transformed awake objective cough frequency, treatment group, week, week*region, week*baseline and week*treatment interactions. Subject will be included as a random effect. The estimated treatment means and differences (orvepitant versus placebo) at Week 12 (primary endpoint) will be reported as part of this analysis, along with 95% confidence intervals and associated p-values. Dose response analyses will be conducted.

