Relevant Screening and Baseline data (i.e. data collected prior to the treatment administration) and demographic characteristics will be summarized descriptively for each treatment group. Efficacy and safety endpoints will be summarized by descriptive statistics for each treatment group and for each time point.

All statistical hypothesis tests and confidence intervals will be two sided, using a type I error rate of 0.05. No adjustment for multiple comparisons will be used for this study.

The primary analysis of log transformed awake objective cough frequency will be conducted via a mixed model for repeated measures (MMRM) with the model including terms for region, baseline log-transformed awake objective cough frequency, treatment group, week, week*region, week*baseline and week*treatment interactions. Subject will be included as a random effect. Dose response analyses will be conducted. The other secondary endpoints will be analyzed using a MMRM except for the global rating of change in cough frequency and in severity which will be analyzed using Mantel-Haenszel methodology.

The safety and tolerability profile will be assessed versus Baseline conditions and differences between treatment groups and descriptive statistics will be produced, where applicable.

Plasma concentrations of orvepitant will be summarized descriptively; possible exposure-response relationships will be explored.

PLANNED DATE OF FIRST SUBJECT ENROLLED

01-Apr-2017

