11.5.2 Secondary Efficacy Analysis

The analysis of change from Baseline in awake objective cough frequency at Weeks 2 and 4 will be conducted as part of the analysis model for the primary endpoint. The analysis of change from Baseline in both 24 hour and night-time (non-waking time) objective cough frequency will be analyzed in the same way as for the primary endpoint. The other secondary endpoints will be also be analyzed using the MMRM except for the global rating of change in cough frequency and in severity. These shall be summarized as categorical endpoints (“worse”, “about the same” and “better”) and analyzed using Mantel-Haenszel methodology. The 7-point scale for degree of change (if they indicate a change) will also be summarized.

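### Primary MMRM: a random subject effect is the only within-subject structure stated; read plainly, it tests Week 12 with a variance averaged over three visits

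*Protocol*

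**What the plan says.** Section 11.5.1 names the primary analysis as an MMRM and lists its fixed effects: region, baseline, treatment group, and "week, week*region, week*baseline and week*treatment interactions". The next sentence is "Subject will be included as a random effect". The synopsis repeats it: "Subject will be included as a random effect. Dose response analyses will be conducted". The protocol says nothing else about dependence between visits. It names no covariance matrix and does not say whether residual variances are equal across visits.

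The primary result is read from this model at one visit: "The estimated treatment means and differences (orvepitant versus placebo) at Week 12 (primary endpoint) will be reported as part of this analysis". Section 11.5.2 carries the approach over, stating that 24-hour and night-time "objective cough frequency will be analyzed in the same way as for the primary endpoint". Section 11.3 leaves further analytical detail to a SAP, which was not available for this review. Section 11.8 makes the handling of missing data depend on a correctly specified model and on data missing at random.

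**The concern.** Had the protocol said nothing about covariance, this would be ordinary SAP detail. It does say something: it puts a random subject effect into the primary model. The usual implementation is a random intercept with independent, constant-variance residuals, which imposes one variance and one correlation on Weeks 2, 4 and 12.

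Every fixed effect is crossed with week, so the means are free to differ by visit while the variance is forced to be common. The three dose-versus-placebo tests at Week 12, each at an unadjusted two-sided 5%, then take their standard error from a variance pooled over visits. If the Week 12 variance is above that average, the tests reject too often and the 95% intervals are too narrow. If it is below, the tests are conservative and some power is lost.

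**Working it through.** **Inputs.** Section 11.1 gives SD of change 0.285 (revised from 0.261), 65 per arm, reductions of 10% and 35%, and two-sided 0.05. Section 11 gives log base 10. The model visits are Weeks 2, 4 and 12 (Section 11.5.1). SDs at Weeks 2 and 4 are not given and are assumed below.

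**1. The plan's own figure.**
- Effect: |log10(0.65/0.90)| = 0.1413.
- Standard error: 0.285 × √(2/65) = 0.0500.
- Power: Φ(0.1413/0.0500 − 1.96) = 80.7% (80.1% with the noncentral t).

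The stated 80% reproduces.

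**2. What the sentence implies.** With random-intercept variance σ²b and residual variance σ²e, the variance at every visit is σ²b + σ²e. With complete data and all fixed effects crossed with week, the Week 12 point estimate equals the one from Week 12 data alone. The REML estimate of the common variance is the mean of the three visit residual variances.

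**3. Effect on the Week 12 test.** Let k be the model standard error divided by the true one:

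k = √[(s₂² + s₄² + s₁₂²)/3] / s₁₂

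- Type I error = 2 × (1 − Φ(1.96k)); coverage = 1 − type I error.
- Power = Φ(0.1413/0.0500 − 1.96k).

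Example with Week 2 and Week 4 SDs of 0.261 and Week 12 SD of 0.285: mean variance = (2 × 0.0681 + 0.0812)/3 = 0.0725, whose root is 0.269. So k = 0.269/0.285 = 0.945, and type I error = 2 × (1 − Φ(1.852)) = 6.4%.

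The 0.024 shift used in the table (0.261 and 0.309) borrows the size of the protocol's SD revision as a yardstick, in both directions. The last two rows are further illustrative pairs.

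| SD at Weeks 2 / 4 (Week 12 = 0.285) | k | Type I error | Coverage | Power | Simulated type I, compound symmetry | Simulated type I, Week 12 variance |
|---|---|---|---|---|---|---|
| 0.285 / 0.285 | 1.000 | 5.0% | 95.0% | 80.7% | 4.8% | 5.0% |
| 0.261 / 0.261 | 0.945 | 6.4% | 93.6% | – | 6.2% | 5.0% |
| 0.309 / 0.309 | 1.057 | 3.8% | 96.2% | 77.5% | 3.8% | 5.0% |
| 0.25 / 0.265 | 0.937 | 6.6% | 93.4% | – | 6.7% | 5.1% |
| 0.31 / 0.30 | 1.047 | 4.0% | 96.0% | 78.1% | 3.8% | 4.9% |

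Power is left blank where the standard error is understated, because the extra rejections are not real power.

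**4. Simulation behind the last two columns.** 20,000 null trials per row with three comparisons each; four arms of 65; region and baseline crossed with visit; assumed between-visit correlations 0.65, 0.55 and 0.60; complete data; t with 254 degrees of freedom; Monte Carlo error about 0.1 point. The Week 12-specific variance stands for the unstructured fit, which gives the same Week 12 standard error with complete data. The equal-SD row has unequal correlations and shows no inflation, so unequal variance is what drives the effect.

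**5. Separate check, including dropout.** Let r be the common SD at Weeks 2 and 4 divided by the Week 12 SD, with correlation 0.6 assumed. Complete data, compound symmetry versus unstructured:
- r = 0.8: 8.5% versus 4.7%
- r = 0.9: 6.8% versus 5.0%
- r = 1.1: 3.6% versus 4.8%

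With about 10% dropout at random, 73 per arm and 1,500 runs (Monte Carlo error about 0.6 points at 5%), r = 0.8 gives 8.3% versus 5.2%.

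**The case against.** The strongest reply is that compound symmetry needs a condition the protocol never states, namely equal residual variances. A random subject effect with visit-specific residual variances also satisfies the sentence and gives Week 12 its own variance parameter. A large-sample, complete-data check of that model, with the same SDs and correlations, brings the two inflated cases to 4.8% and 4.9%. This stands, and it shows that the inflation comes from the default residual assumption rather than from the random effect alone. But the same model gives 4.3% with equal SDs and about 3.9% in the falling-variance cases, because it still forces one common covariance between every pair of visits. Neither implementation does better than an unstructured matrix.

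Second, the covariance could be left to the SAP, as degrees of freedom can. The SAP may indeed name an unstructured matrix. The protocol sentence would then be redundant or in conflict, since a random intercept added to an unstructured matrix is not separately identifiable.

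Third, the numbers are hypothetical. That is correct: the protocol reports no SD by visit, and the 0.024 shift concerns a planning SD, not a difference between visits. In addition, 0.285 is the SD of change while the model adjusts for baseline, so the power figures describe the two-sample planning calculation rather than the MMRM. The type I figures depend only on the ratios between visit SDs.

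Fourth, a drift of about 1.4 points is modest in an exploratory study that openly leaves three comparisons unadjusted. That is fair, and it limits the weight of the point.

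**Conclusion.** The point holds as an inexpensive improvement, with medium confidence. The only within-subject structure the protocol states is, in its ordinary form, compound symmetry, which bases the Week 12 tests on a visit-averaged variance. In the closed-form examples, per-comparison type I error runs from 3.8% to 6.6% instead of 5%. There is no distortion if the three visit variances are equal.

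This rests on assumed SDs at Weeks 2 and 4, on the default reading of the random effect, and for the closed-form figures on complete data. It shows a risk of either sign, not an established inflation. The planned 65 per arm is unaffected, because it comes from a two-sample calculation with one SD. No claim is made about the questionnaire models, for which the random effect is not restated.

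**What to change.** Before unblinding, replace the sentence in the synopsis and Section 11.5.1 with wording such as:

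> Within-subject errors will be modelled with an unstructured covariance matrix over Weeks 2, 4 and 12, fitted by REML, with no additional random subject effect.

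Section 11.5.2 then carries this to 24-hour and night-time cough frequency. Align the SAP; if it already says this, only the protocol sentence has to change. The degrees-of-freedom method, the fallback if the fit does not converge, and the questionnaire models can stay in the SAP.

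The statistical cost is six covariance parameters instead of two, with three visits and about 260 completers. No new data are needed and the sample size stays the same. The administrative cost is a protocol amendment. Under Section 14.1 it needs regulatory and ethics authorization unless the sponsor deems it administrative.
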